9. PRIMARY OBJECTIVE

The primary objective is to determine the activity of a combination of LEN with MOR00208 in terms of best objective response rate (ORR = rate of patients with complete response [CR] or partial response [PR]) in adult patients with R-R DLBCL.

9.1 Endpoint: Best objective response rate

The best ORR is defined as the proportion of patients with CR or PR as best response achieved at any time during the study. The denominator will be the total number of patients included in the analysis population.

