Patients should not have received a CD20-targeted therapy, chemotherapy, radiotherapy, investigational anticancer therapy or other lymphomaspecific- therapy within 14 days prior to Cycle 1 day 1 of the study. In addition, no radiotherapy (including limited field radiotherapy) is permitted after the baseline PET/CT scan for initial disease assessment has been performed. Other than the study drugs, patients should not receive any other DLBCLspecific- therapy during the study treatment period. The patient should not receive any investigational agent other than MOR00208 and LEN during the treatment period of the study.

The use of concurrent antineoplastic therapies other than study drugs, including, but not limited to, chemotherapies, hormonal therapy, immunotherapy, biological response modifiers, mAbs with or without conjugation, radioisotopic therapies, stem cell transplant and targeted small molecules are not permitted during the entire treatment period (i.e., prior to disease progression during this study) of this study. After disease progression has been recorded, additional antineoplastic therapies are permitted at the discretion of the investigator and in accordance with the local guidelines and should be recorded in the eCRF.

Systemic Glucocorticosteroids

The use of systemic glucocorticosteroids is generally discouraged because their potential antilymphoma activity in patients with DLBCL may confound interpretation of antitumor effects mediated by study drug treatment (MOR00208 and LEN).

However systemic corticosteroids in doses up to 20 mg/day prednisone or equivalent (i.e. equipotent corticosteroid) are permitted, provided the dosing is stable (not increased within the last month), but only for the treatment of non-neoplastic comorbid indications (e.g. rheumatoid arthritis).

-Screening:

Patients may potentially receive systemic glucocorticosteroids in doses above 20 mg/day (prednisone or equivalent) to manage severe DLBCL manifestations (e.g., compressive disease, rapidly progressing symptomatic adenopathy) during Screening as per institutional standards. For these patients the glucocorticosteroids treatment needs to be tapered to a total daily dosage of 20 mg or less of prednisone or its equivalent prior to study drug(s) administration on Cycle 1, Day 1.

-Cycle 1 through EOT visit:

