The same scan modality should be used for all assessments, and all patients are required to have scans of the neck/chest/abdomen/pelvis. All scans conducted during the study will be provided to a central imaging laboratory for independent radiological and clinical evaluation.

If it is impossible for the patient to have their PET examination in fasted state, adequate procedures should be in place to measure and control blood glucose level.

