5.3 Determination of sample size

Approximately 80 patients with R-R DLBCL who meet all of the inclusion criteria and have none of the exclusion criteria will be enrolled into the study. The study will be performed with an interim stop for the evaluation of the safety of the LEN dosage. No adjustment of sample size or adaptation of efficacy evaluations will be made at this point. As the primary purpose of this study is to evaluate the clinical efficacy of 25 mg daily oral LEN combined with 12 mg/kg MOR00208 administered by IV infusion in patients with R-R DLBCL, no formal statistical hypothesis testing will be performed.

**STATISTICAL ANALYSIS PLAN**MorphoSys AG
MOR208C203

For the determination of a suitable sample size, it is assumed that the combination treatment could improve the ORR of LEN from a value of 20% (under monotherapy) to 35% (under combination therapy). Applying an exact binomial test with a two-sided significance level of 5% and a power of 85% the estimated sample size is 73 patients (calculation performed by nQuery Advisor® 7.0). According to this scenario an observed ORR of 32% would lead to the conclusion that the outcome is statistically superior to outcomes observed previously for the monotherapy. Assuming a drop-out rate of 10%, a total sample size of about 80 patients is estimated.

The sample size determination has been conducted using various possible monotherapy and combination effect ORR rates and various power assumptions. Literature evaluation of study results concerning the ORR rates of LEN or comparable products (as mono- or combination therapy) as well as study results for MOR00208 ongoing studies were used to justify assumptions on response rates (Witzig et al., 2011; Wang et al., 2013).

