8.7.6 Non-study anti-DLBCL treatment

Data on non-study anti-DLBCL treatments will be provided for patients who are still on any study drug, and for patients who have already discontinued the treatment (based on the ‘*Other Anti-Neoplastic Therapies after end of Study Drug Treatment*’ and “*Concurrent Anti-Neoplastic Therapies Medications*” eCRF pages). The following summaries will be presented for both the FAS and the SAF:

- The number (%) of patients who received non-study cancer treatment prior to study treatment discontinuation.
- The number (%) of patients who received non-study cancer treatment after study treatment discontinuation.
- The number (%) of patients who received non-study cancer treatment without a documented radiological progression as per CHESON Criteria.
- The type of anti-cancer treatment received by ATC level 2 class and preferred name.
- Time to start of non-study anti-cancer treatment.
- Therapy line of non-study anti-cancer treatment.
- Reason for stopping non-study anti-cancer treatment.

Time to start of anti-cancer therapy is defined as (start date of anti-cancer treatment – date of last dose of study treatment + 1). In case the anti-cancer therapy started before the last dose of study treatment the time will be set to zero. If the start date of anti-cancer treatment is missing, then the time to start of anti-cancer treatment for that patient will be missing. Listings on other non-study cancer treatments will be presented for the SAF.

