9.2 Main analysis

The number and percentage of patients classified as having best overall response of CR or PR as well as 95% confidence limits (using the Clopper-Pearson exact method) will be presented. The number and percentage of patients with CR, and the number and percentage of patients with PR as best response will be shown. The main analysis will be conducted on the FAS for both the IRC response assessment, and the local, i.e., investigator (INV) response assessment.

For the main analysis of best ORR:

- The tumour assessments will be derived according to the IWG treatment response criteria for malignant lymphoma (Cheson et al., 2007; see Section 6.14), by an Independent Radiology/Clinical Review Committee (IRC). The review process will be defined in the IRC Charter.
- Patients with no post-baseline assessment of response will be included as non-responders.

-
- Patients with a best response of “Not Evaluable” will be summarized by reason for having unknown status. The following reasons will be used:
 - No valid post-baseline assessment available.
 - All post-baseline assessments have overall response “Unknown” or “Not evaluable” or “Indeterminate”.
 - New anti-cancer therapy started before first post-baseline assessment.
 - No formal hypothesis testing will be conducted.

The main analysis will be performed using the FAS.

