**Table 13: Censoring Rules**

Situation	Date of Progression or Censoring	Outcome	Censoring reason
Ongoing and No event until data cut-off	Date of last adequate tumour assessment	Censored	Ongoing
Discontinued the study with no event	Date of last adequate tumour assessment	Censored	Discontinued without event
No baseline tumour assessment	Date of C1D1	Censored	No baseline tumour assessment
Lost to follow-up	Date of last IRC tumour assessment (or C1D1 in case of study discontinuation w/o progression before any post-baseline assessment)	Censored	Lost to follow-up
Patient received non-study anti-DLBCL treatment before disease progression	Date of last adequate tumour assessment before start of non-study cancer treatment	Censored	New anti-cancer therapy started
Clinical Progression*	Date of last adequate tumour assessment	Censored for Analysis based on Investigator assessment only	Clinical Progression not validated by Cheson Criteria
PD by modality not including PET Scan is not confirmed by modality including PET Scan**.	Date of last adequate tumour assessment	Censored for Analysis based on Investigator assessment only	Non-PET PD not confirmed by PET.
Death before any date of PD assessment	Date of death	Progressed	
Death between adequate assessments	Date of death	Progressed	
Death or progression after two or more	Date of last adequate	Censored	Event documented

STATISTICAL ANALYSIS PLAN

 MorphoSys AG
 MOR208C203

Situation	Date of Progression or Censoring	Outcome	Censoring reason
missed visits	tumour assessment		after two or more missing tumor assessments
EOT after two or more missed assessments without disease progression	Date of Last adequate Tumour Assessment	Censored	Adequate assessment no longer available

Abbreviations: EOT = End of Treatment; IRC = Independent Review Committee; PD = progressive disease; CT = Computed tomography; PET = Positron emission tomography. *Progression as per Investigator's assessment and without meeting PD criteria according to Response Criteria for Malignant Lymphoma (Cheson et al., 2007). **The rule only applies in case a PET-including modality is performed after a non-PET including modality.

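### The SAP's primary ORR stops neither at progression nor at non-study anti-lymphoma therapy, unlike PFS, DoR and TTP, so a response first seen after such therapy can be counted

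*SAP*

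**What the plan says.** SAP section 9.1 makes the primary endpoint the "proportion of patients with CR or PR as best response achieved at any time during the study". Table 1 in SAP section 4 describes the same endpoint with a window that covers both treatment and follow-up. Protocol section 10.6.1 and the synopsis are narrower: on central evaluation, a CR or PR counts only until progression.

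Within the ORR analysis, the SAP mentions other treatment once. Section 9.2 lists reasons for a Not Evaluable best response, one of which is "New anti-cancer therapy started before first post-baseline assessment".

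The time-to-event endpoints handle the event explicitly. For a patient given non-study treatment before progression, Table 13 sets the PFS censoring date as "Date of last adequate tumour assessment before start of non-study cancer treatment". DoR (section 10.3.3) uses the same table, and TTP (section 10.5.2) is also censored for new antineoplastic therapy.

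The SAP expects such patients. Section 8.7.6 will tabulate "The number (%) of patients who received non-study cancer treatment prior to study treatment discontinuation", and separately those treated without radiologically documented progression. Protocol section 6.7 bars other lymphoma therapy during study treatment before progression, then relaxes the bar: "After disease progression has been recorded, additional antineoplastic therapies are permitted at the discretion of the investigator".

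**The concern.** In a single-arm trial the response window carries the whole attribution argument, because no control arm absorbs responses to other treatment. The authors recognised non-study therapy as an event that ends the evaluable period for PFS, DoR and TTP, and covered one special case for ORR. The general case has no rule: an evaluable scan without response, then other therapy, then a response. The literal text counts that response in the primary endpoint.

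Two things are at stake. The ORR could include a response that cannot be ascribed to the study combination. ORR and DoR would also use different windows in the same responders, so the programmer would have to make an unwritten choice.

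**Working it through.** **1. The rules side by side**

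| Endpoint | Place | Ends at progression? | Non-study therapy |
|---|---|---|---|
| ORR | Protocol 10.6.1 | Yes | No rule |
| ORR | SAP 9.1, Table 1, 9.2 | No | Addressed only if begun before the first post-baseline assessment |
| DCR | SAP 10.1.2, 10.1.3 | No | As for ORR |
| PFS | SAP Table 13 | Yes (event) | Censored at last adequate assessment before it |
| DoR | SAP 10.3.3, via Table 13 | Yes (event) | As for PFS |
| TTP | SAP 10.5.2 | Yes (event) | Censored |

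**2. One patient followed through the rules**

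Take SD at Cycle 3 Day 1 (nominal day 2×28+1 = 57), non-study therapy in Cycle 4 without documented progression, and CR at Cycle 5 Day 1 (day 4×28+1 = 113).

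- The Cycle 5 scan is still scheduled. The note to SAP Table 12 continues assessments to progression, death or study discontinuation, and does not name new therapy as a stop.
- The scan reaches the central readers. Protocol section 7.2.14.1 says: "All scans conducted during the study will be provided to a central imaging laboratory for independent radiological and clinical evaluation".
- ORR: responder under section 9.1. Section 9.2 does not apply, because a post-baseline assessment came before the therapy.
- DoR starts at the first CR or PR (SAP 6.9), day 113. It is censored at the last adequate assessment before the therapy (Table 13), day 57. With the formula in SAP 10.3.2, DoR = 57 − 113 + 1 = −55 days.

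**3. The plan's own figure**

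SAP section 5.3: "Applying an exact binomial test with a two-sided significance level of 5% and a power of 85% the estimated sample size is 73 patients". The reference and target ORR are 20% and 35%.

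n = [(1.960×√(0.20×0.80) + 1.036×√(0.35×0.65)) / 0.15]² = [(0.7840 + 0.4943) / 0.15]² = 72.6, rounded up to 73.

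The smallest significant count at N=73 is 23/73 = 31.5% (exact upper tail 0.0135), which matches the stated 32%. The formula that returns 73 is the normal approximation rather than the exact test; that is a separate matter. The response window does not enter this calculation, so the sample size is unaffected.

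**4. Size at N=80**

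Each reclassified patient moves the ORR by 1/80 = 1.25 points. The documents give no count, so I assume k = 0 to 5 patients, which is 0 to 6.25 points.

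Clopper-Pearson 95% limits (the method in SAP 9.2):

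- 24/80 = 30.0%: 20.3% to 41.3%, excludes 20%.
- 23/80 = 28.8%: 19.2% to 40.0%, does not.

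**5. Chance of reaching 24/80 when the other patients respond at 20%**

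If k patients are credited with a response to other therapy, the chance is P(Binomial(80−k, 0.20) ≥ 24−k):

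| k (assumed) | 0 | 1 | 2 | 3 | 4 | 5 |
|---|---|---|---|---|---|---|
| Chance | 2.2% | 3.4% | 5.2% | 7.7% | 11.1% | 15.6% |

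**The case against.** The conduct rules leave little room for the problem, and most of that case stands.

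- **Other therapy is restricted.** Protocol section 6.7 bars other lymphoma therapy before progression, and any radiotherapy after the baseline PET/CT. The patient in the working is therefore a protocol deviation.
- **The PPS may help.** ORR is repeated on the PPS (SAP 9.3), which would remove such a patient, but only if the deviation is classed as major. That analysis is supportive, and no sensitivity analysis targets this event.
- **Section 9.2 points the right way.** Its Not Evaluable reason makes sense only if scans after new therapy are disregarded. That suggests the intent but leaves the general rule unwritten. The IRC Charter may limit the reading window; it is not among the documents.
- **No formal test is planned.** The interval comparison with 20% is an interpretation, not a decision rule.

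A reader might go further and infer that patients kept on MOR00208 past progression, with another drug added, will feed responses into the ORR. The documents do not support this as a routine event. Footnote 17 to protocol Table 5 removes the routine scans for these patients, and SAP Table 12 ends assessments at progression, so an off-schedule scan would be needed. Nor would these patients have a negative DoR for this reason, because the Table 13 row applies only to therapy started before progression.

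The reference to follow-up in Table 1 also adds almost no scans. Survival follow-up is by telephone, and SAP section 20.9 states that PFS is not followed after treatment ends.

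**Conclusion.** The gap is real and lies in the stated primary-endpoint rule. SAP 9.1 and Table 1 drop the protocol's progression limit and set no stop at non-study therapy, while PFS, DoR and TTP have one. Followed literally, the rule can count a response first seen after other therapy, and it gives that patient a DoR that ends before it starts.

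It would be tempting to conclude that responses to other treatments are in fact being credited to the combination. The documents do not show that. Section 8.7.6 tabulates who received other therapy, not who responded afterwards, and the conduct rules make such cases uncommon. This is a missing rule and an inconsistency between endpoints, not a demonstrated misattribution.

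The size is 1.25 points per patient at N=80. The range of 0 to 5 patients is an assumption, and zero is possible. It matters mainly if the result falls near 24 of 80, where one response decides whether the interval excludes 20%.

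**What to change.** In SAP 9.1, Table 1 and 10.1.2, state that:

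- best response, by IRC or investigator, uses only assessments up to the earlier of documented progression and the start of any non-study anti-lymphoma therapy (drug, radiotherapy, surgery or transplant);
- patients without CR or PR by then are non-responders and stay in the FAS denominator;
- the same window applies to the CR rate, time to response and the start of DoR.

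Keep the any-time rate as a sensitivity analysis in section 9.3, so that the effect of the window is visible.

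The cost is a few sentences and one date filter in the response dataset. Start dates of other therapy are already needed for Table 13 and for event-free survival (SAP 16.4.2). The sample size does not change. The downside is that the reported ORR may be slightly lower.

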9.2 Main analysis

The number and percentage of patients classified as having best overall response of CR or PR as well as 95% confidence limits (using the Clopper-Pearson exact method) will be presented. The number and percentage of patients with CR, and the number and percentage of patients with PR as best response will be shown. The main analysis will be conducted on the FAS for both the IRC response assessment, and the local, i.e., investigator (INV) response assessment.

For the main analysis of best ORR:

- The tumour assessments will be derived according to the IWG treatment response criteria for malignant lymphoma (Cheson et al., 2007; see Section 6.14), by an Independent Radiology/Clinical Review Committee (IRC). The review process will be defined in the IRC Charter.
- Patients with no post-baseline assessment of response will be included as non-responders.

-
- Patients with a best response of “Not Evaluable” will be summarized by reason for having unknown status. The following reasons will be used:
 - No valid post-baseline assessment available.
 - All post-baseline assessments have overall response “Unknown” or “Not evaluable” or “Indeterminate”.
 - New anti-cancer therapy started before first post-baseline assessment.
 - No formal hypothesis testing will be conducted.

The main analysis will be performed using the FAS.

9.3 Sensitivity analyses

- The main analysis as described in Section 9.2 will be conducted based on the INV assessment.
- The main analysis as described in Section 9.2 will be conducted using the PPS (based on INV and IRC assessment).
- The analysis as described in Section 9.2 will be performed excluding the patients with no post-baseline assessment of response or with all post-baseline assessments categorized as “Unknown”. The analysis will be performed using the FAS based in both IRC and INV assessment.
- The number (%) of patients will be descriptively tabulated by categories of individual best outcome in tumor response assessments (CR, PR, SD, PD, Not Evaluable). Listings will be generated for both central and local response assessments (for the SAF).

9.4 Concordance between IRC and investigator (INV) assessment

The concordance rate in terms of response assessment represents the agreement in the best overall outcome (CR, PR, SD, PD, Not Evaluable, and Not Available) in tumour response assessments between the IRC and INV assessment. The concordance rate is the number of patients that are concordant over the total number of patients assessed, and will be calculated across all response categories. A contingency table will be generated. The concordance rate is calculated by adding the diagonal counts and dividing by the total number of patients assessed. Moreover, the agreement (%) of the INV assessment by the IRC in terms of best ORR will be calculated (i.e., the proportion of patients with a best response of CR or PR by investigator assessment that have a confirmed best response of CR or PR by the IRC assessment).

Patients who have been evaluated by investigator assessment, but not by central review assessment will be excluded from the concordance analysis.

The proportion (%) of patients who had at least one central review among the total number of patients who underwent at least one INV assessment will be calculated. Moreover, the proportion (%) of the total number of central reviews among the total number of INV assessments will be derived (i.e., the total number of central reviews across all visits and all patients divided with the total number of investigator response assessments across all visits and all patients multiplied by 100). The analysis will be conducted using the FAS.

10. SECONDARY OBJECTIVES

10.1 Secondary objective 1

10.1.1 Objective

To determine the activity of a combination of LEN with MOR00208 in terms of disease control rate (DCR = complete response (CR) + partial response (PR) + stable disease (SD) as best objective response) in adult patients with R-R DLBCL.

10.1.2 Endpoint: Disease control rate

DCR is defined as the proportion of patients having CR, PR or SD based on the best objective response achieved at any time during the study. The denominator will be the total number of patients included in the analysis population.

10.1.3 Main analysis

The number and percentage of patients classified as having best overall response of CR or PR or SD as well as 95% confidence limits (using Clopper-Pearson exact method) will be presented. The number and percentage of patients with CR, the number and percentage of patients with PR and the number and percentage of patients with SD as best response will be presented. The main analysis will be conducted on the FAS for the both IRC and INV response assessments.

For the main analysis of DCR:

- The tumour assessments will be derived according to the IWG treatment response criteria for malignant lymphoma (Cheson et al., 2007; see Appendix), by an Independent Radiology/Clinical Review Committee (IRC). The review process will be defined in the IRC Charter.
- Patients with no post-baseline assessment of response will be included as non-responders.
- Patients with a DCR of “unknown” will be summarized by reason for having unknown status. The following reasons will be used:

-
- No valid post-baseline assessment.
 - All post-baseline assessments have overall response “Unknown” or “Not evaluable”.
 - New anti-cancer therapy started before first post-baseline assessment.
 - No formal hypothesis testing will be conducted.

